# Table 3.4.3-1 Exclusion Criteria Rollover Subjects from Trial 331-201-00080 or 331-201-00081 30. Subjects with a major protocol violation during the course of their participation in the double-blind phase 3 trial (ie, Trial 331-201-00080 or 331-201-00081). Minor violations such as occasional visits outside of the acceptable window or a missing blood draw will not exclude a subject from participation in Trial 331-201-00083; however, continual lack of compliance with the visit schedule, trial assessments, or treatment regimen in the prior double-blind trial would be considered a major violation that would result in exclusion from Trial 331-201-00083. The medical monitor should be contacted if the investigator is unsure of a subject's eligibility.

AE = adverse event; ALT = alanine aminotransferase; AST = aspartate aminotransferase; BMI = body mass index; CPK = creatine phosphokinase; C-SSRS = Columbia-Suicide Severity Rating Scale; DBP = diastolic blood pressure; ECG = electrocardiogram; HbA1c = glycosylated hemoglobin; HIV = human immunodeficiency virus; IDDM = insulin dependent diabetes mellitus; OTC = over-the-counter; QTcF = QT interval as corrected by Fridericia's formula; SBP = systolic blood pressure; T4 = free thyroxine; ULN = upper limit of normal; WOCBP = women of childbearing potential.

Nonchildbearing potential is defined as male and female subjects who are surgically sterile (ie, male subjects who have undergone bilateral orchidectomy and female subjects who have undergone bilateral oophorectomy and/or hysterectomy) and female subjects who have been postmenopausal for at least 12 consecutive months.

Subjects must agree to restrictions to medications and lifestyle as described in Section 4.

Subjects with a positive blood alcohol screen should be reassessed for alcohol abuse and dependence before consultation with medical monitor about approval for inclusion. Subjects with a positive drug screen that, in the judgment of the investigator with concurrence of the medical monitor, could compromise the subject's safety or ability to comply with the trial procedures that could interfere with the interpretation of trial results should be excluded from the trial. Subjects with a positive drug screen for cocaine or other illicit drugs are excluded and may not be retested or rescreened. Subjects with a positive urine drug screen resulting from use of marijuana, prescription, or overthe-counter (OTC) medications or products that in the investigator's documented opinion do not signal a clinical condition that would impact the safety of the subject or interpretation of the trial results or the subject does not meet DSM-5 criteria for substance abuse or dependence, may continue evaluation for the trial following consultation and approval by the medical monitor.

Screen failures may be rescreened at any time if the exclusion characteristic has changed. Subjects who sign an ICF but who are not started on treatment are permitted to be rescreened. If a subject is rescreened for trial participation, and the rescreening is not completed within the original screening window, a new ICF must be signed.

Confidential - Proprietary Information

32

<sup>aThe enrollment of de novo subjects at any site will not be permitted until initiation and notification by the sponsor.

[figure not shown]
#### 3.5 Endpoints

# 3.5.1 Primary Endpoint

The primary endpoint is the safety and tolerability of brexpiprazole (OPC-34712), as assessed by the frequency and severity of adverse events (AEs).

# 3.5.2 Secondary Endpoints

None.

Confidential - Proprietary Information

33

#### 3.5.4 Additional Safety Endpoints

Standard safety variables will include clinical laboratory tests (hematology, serum chemistry [including prolactin and glycosylated hemoglobin (HbA1c)], coagulation parameters, and urinalysis), physical examinations, vital sign measurements, and electrocardiograms (ECGs). Body weight, height, and waist circumference will also be measured.

#### 3.6 Measures to Minimize/Avoid Bias

This trial is open-label.

#### 3.7 Trial Procedures

This is a multicenter, open-label trial designed to assess the safety and tolerability of oral brexpiprazole (OPC-34712) (2-4 mg/day) as treatment in adults with bipolar I disorder. The trial will be conducted on an outpatient basis. The trial comprises a 26-week open-label treatment period with a 21 ( $\pm$  2) day follow-up.

Trial assessment time points are summarized in Table 3.7-1 (open-label treatment phase [Phase B]) and Table 3.7-2 (conversion phase [Phase A]).

34

Table 3.7-1	Schedule	of Assessm	ents - O	pen-label	Treatmen	nt (Phase	B)			
Assessment	Screening	Phase B	Open-Label Treatment Phase Trial Week Visit (± 2 days)				/s)	Follow-up		
	Baseline a (Rollover)	Baseline a (De Novo)	1	2	4	8	12	18	26 / ET b	21 (± 2) days c
ENTRANCE CRITER				_	,					
Informed consent	$\mathbf{X}^{\mathbf{d}}$									
Inclusion/exclusion criteria	X	X								
Medical history	Xe									
CCI		 			I.		1	1	- I	
			_		-					
SAFETY				 	· L			1		I
Physical examination	X f	X g							X	
Waist circumference	X f	X g							X	
Vital signs i	X f	X g	X	X	X	X	X	X	X	
12-lead ECG j	X f	X g					X		X	
Clinical laboratory tests k	X f,l	X g,l					X m		X m	
HbA1c	X f,l	$X^{g,l}$					X m		X m	
Drug screen/blood alcohol n	X f	X g			X		X		X	
Urine pregnancy test (WOCBP only) 	X f	X g	X	X	X	X	X	X	X	
CCI										

Confidential - Proprietary Information

35

Table 3.7-1				P		ıt (Phase ]				
Assessment	Screening	Phase B	Open-Label Treatment Phase Trial Week Visit (± 2 days)						Follow-up	
	/	Baseline a								21 (± 2) days
	Baseline a	(De								
	(Rollover)	Novo)	1	2	4	8	12	18	26/ ET b	
CCI										
Adverse events q	X	X	X	X	X	X	X	X	X	X
Concomitant medications	X	X	X	X	X	X	X	X	X	X
OTHER		•		•			•	•		•
CCI										
										
					•					
Dose adjustment r			X	X	X	X	X	X	X	
Register visit in IWRS	X	X	X	X	X	X	X	X	X	
IMP dispensing	X	X	X	X	X	X	X	X		
IMP accountability			X	X	X	X	X	X	X	

<sup>aFor rollover subjects, screening for Trial 331-201-00083 occurs simultaneously with baseline which will be at the same day as the Day 21 (Week 3) visit of Trial 331-201-00080 or Trial 331-201-00081. Separate screening and baseline visits are required for de novo subjects to allow for completion of eligibility assessments and washout of prohibited concomitant medications, if applicable. The enrollment of de novo subjects at any site will not be permitted until initiation and notification by the sponsor.

Confidential - Proprietary Information

36

<sup>bIf a subject discontinues early before Week 26, procedures noted for Week 26 must be completed at the ET visit. Attempts should be made to complete ALL evaluations, particularly efficacy assessments, for the Week 26/ET visit prior to the administration of any new psychotropic medications. However, if the subject receives a new antipsychotic prior to ET procedures, no efficacy assessments should be done. Any prohibited medications started before the end of the trial assessments should be documented as a protocol deviation in the source notes.

<sup>gBaseline assessment will be performed at baseline of Phase B for de novo subjects who enter Phase B directly after screening, but will be obtained from the Conversion Week 4 visit of Phase A for subjects who participate in Phase A.

Vital signs include body weight, body temperature, systolic blood pressure (SBP), diastolic blood pressure (DBP), and heart rate. Blood pressure and heart rate will be measured in the following order: supine and standing after the subject has been in each position for at least 3 minutes. Vital signs scheduled for the same visit as blood samples are to be completed before blood is drawn.

jStandard 12-lead ECGs will be performed after the subject has been supine and at rest for ≥ 5 minutes prior to the ECG. A central ECG service will be utilized to review all ECGs in order to standardize interpretations for the safety analysis. However, ECG results will also be evaluated at the investigational site to monitor safety during the trial. Rollover subjects will be enrolled in Trial 331-201-00083 based on the screening/baseline ECG results from the trial site. If the screening/baseline ECG results from the central reader, when available, indicate a QT interval corrected for heart rate using Fridericia's formula (QTcF) ≥ 450 msec in men and ≥ 470 msec in women, unless due to ventricular pacing at screening/baseline, the investigator must contact the medical monitor to discuss the subject's continued participation in the trial. For de novo subjects, ECG results from the central reader must be reviewed for exclusion criteria prior to the first dose of open-label brexpiprazole in Phase B. Any ECGs scheduled for the same visit as blood samples are to be completed before blood is drawn.

kIncludes hematology (including prothrombin time [PT], activated partial thromboplastin time [aPTT], and international normalized ratio [INR]), serum chemistry (including prolactin, HbA1c, and thyroid-stimulating hormone [TSH], with reflex to free thyroxine [T4] if the result for TSH is abnormal), and urinallysis.

Rollover subjects must be fasting for a minimum of 8 hours prior to blood draws for screening/baseline laboratory assessments, if at all possible. If fasting blood samples are not feasible at screening, nonfasting blood samples may be obtained initially for determining eligibility for the trial. A fasting blood sample is required at baseline prior to dosing. De novo subjects must fast for a minimum of 8 hours prior to blood draws for baseline laboratory assessments.

mBlood samples for clinical laboratory tests must be drawn after a minimum 8-hour fast at Week 26/ET and should be drawn after a minimum 8-hour fast at all other visits, if possible. Vital sign and ECG assessments should be completed before any blood samples are collected.

Confidential - Proprietary Information

37

<sup>cConsists of telephone contact or clinic visit (investigator's discretion) for evaluation of safety and applies to all subjects (completers and premature withdrawals).

<sup>dInformed consent for Trial 331-201-00083 will occur at screening/baseline for rollover subjects and must be obtained before any trial-related procedures specific to the open-label trial are performed.

<sup>eUpdate, if necessary, for rollover subjects.

<sup>fScreening/baseline value will be obtained from the Day 21 (Week 3) visit of Trial 331-201-00080 or Trial 331-201-00081.

Until the information herein is released by Otsuka to the public domain, the contents of this document are Otsuka confidential information and should not be duplicated

<sup>nA urine drug screen and a blood alcohol test are required at the designated times, but either or both can be conducted at any time during the trial at the discretion of the investigator. If results of either or both are positive, the investigator must contact the medical monitor to discuss the subject's eligibility for continued participation in the trial.

OAll positive urine pregnancy test results must be confirmed by a serum test. Subjects with positive urine and serum pregnancy test results at screening, baseline, or screening/baseline must not be enrolled in Trial 331-201-00083. Subjects with positive urine and serum pregnancy test results during the trial must discontinue treatment and be withdrawn from the trial. Pregnancy tests can be performed at any point during the trial if pregnancy is suspected.

<sup>qAE recording will begin with the signing of the ICF for Trial 331-201-00083.

<sup>rAdjustments to the dose of brexpiprazole can be made at scheduled and unscheduled visits during the 26-week open-label treatment phase (ie, Phase B) to optimize efficacy and tolerability as described in the protocol. Subjects must return to the clinic for unscheduled visits if dose adjustments for brexpiprazole are required between scheduled visits.

Schedule of Assessments - Screening and Conversion (Phase A): De Novo Subjects **Table 3.7-2** The enrollment of de novo subjects at any site will not be permitted until initiation and notification by the sponsor. Conversion Week 4/ Phase B Conversion Conversion Conversion Baselineb Screening Week 1 Week 2 Week 3 Phase A  $(Days - 14 to - 1)^{a}$ (± 2 days) Assessment **Baseline** (± 2 days) (± 2 days) (± 2 days) ENTRANCE CRITERIA X Informed consentc Inclusion/exclusion criteria Medical history  $\mathbf{X}$ Demography  $\mathbf{X}$ Psychiatric history MINI Prior medication washoutd X HIV, HBsAg, and anti-HCV X **SAFETY** X  $\mathbf{X}$ Physical examinatione Waist circumference X X X X X X X Vital signsf 12-lead ECGg X X Clinical laboratory tests (hematology, Xi X serum chemistry [including prolactin], and urinalysis)h  $\mathbf{X}^{\mathbf{i}}$ TSH with reflex to free T4 if abnormalh X

Confidential - Proprietary Information

39

Table 3.7-2 Schedule of	Assessments - Screen	ing and Conv	ersion (Phase A	): De Novo Sul	bjects	
The enrollment of o	de novo subjects at any site	will not be perm	itted until initiation	and notification by	the sponsor.	
Assessment	Screening (Days -14 to -1) a	Phase A Baseline	Conversion Week 1 (± 2 days)	Conversion Week 2 (± 2 days)	Conversion Week 3 (± 2 days)	Conversion Week 4/ Phase B Baseline b (± 2 days)
HbA1c h	X i	X				X
PT, aPTT, and INR h	X	X				X
Drug screen/blood alcohol j	X					X
Urine pregnancy test (WOCBP only) k	X					X
CCI						
			_			
Adverse events	X m	X	X	X	X	X
Concomitant medications n	X	X	X	X	X	X
OTHER						
CCI						
_						
Register visit in IWRS	X	X	X	X	X	X
Cross-titration 		X	X	X	X	X
IMP dispensing		X	X	X	X	X
IMP accountability			X	X	X	X

HBsAg = hepatitis B surface antigen; HCV = hepatitis C virus.

Confidential - Proprietary Information

40

<sup>aAll de novo subjects (ie, subjects who did not participate in one of the double-blind phase 3 trials) will enter a screening period to determine eligibility for the open-label trial. Screening begins when the ICF is signed and will take place between Day -14 and Day -1; however, screening procedures should be initiated

with a sufficient amount of time allotted in order to obtain laboratory results prior to baseline. Review of inclusion/exclusion criteria at baseline will be based on some assessments performed during screening.

bIf a subject discontinues early before Week 4, procedures noted for Week 26/ET must be completed at the ET visit. Attempts should be made to complete **ALL** evaluations, particularly efficacy assessments for the Week 26/ET visit prior to the administration of any new psychotropic medications. However, if the subject receives a new antipsychotic prior to ET procedures, no efficacy assessments should be done. Any prohibited medications started before the end of the trial assessments should be documented as a protocol deviation in the source notes.

cInformed consent must be obtained before any trial-related procedures are performed.

dWashout of prohibited medications begins after signing the ICF. Details of medications requiring washout are provided in Section 4.1. Prohibited and restricted medications are also provided in Section 4.1. In addition, all antipsychotic medications used within 30 days of the first dose of IMP will be recorded.

eTo include measurement of height at screening only.

fVital signs include body weight, body temperature, SBP, DBP, and heart rate. Blood pressure and heart rate will be measured in the following order: supine and standing after the subject has been in each position for at least 3 minutes. Vital signs scheduled for the same visit as blood samples are to be completed before blood is drawn.

[figure not shown]
gStandard 12-lead ECGs will be performed after the subject has been supine and at rest for ≥ 5 minutes prior to the ECG. A central ECG service will be utilized to review all ECGs in order to standardize interpretations for the safety analysis. However, ECGs will also be evaluated at the investigational site to monitor safety during the trial. Any screening ECG with abnormal result(s) considered to be clinically significant should be repeated to confirm the finding(s) before excluding the subject from the trial. ECGs scheduled for the same visit as blood samples are to be completed before blood is drawn.

hBlood samples for clinical laboratory tests must be drawn after a minimum 8-hour fast at screening and Conversion Week 4, if at all possible. If fasting blood samples are not feasible at screening, nonfasting blood samples may be obtained initially for determining eligibility for the trial. Vital sign and ECG assessments should be completed before any blood samples are collected.

iSee Section 3.4.3 for exclusions based on screening laboratory results.

jA urine drug screen and a blood alcohol test are required at the designated times, but either or both can be conducted at any time during the trial at the discretion of the investigator. If results of either or both are positive, the investigator must contact the medical monitor to discuss the subject's eligibility for continued participation in the trial.

kAll positive urine pregnancy test results must be confirmed by a serum test. Subjects with positive urine and serum pregnancy test results at screening must not be enrolled. Subjects with positive urine and serum pregnancy test results during the trial must discontinue treatment and be withdrawn from the trial. Pregnancy tests can be performed at any point during the trial if pregnancy is suspected.

Confidential - Proprietary Information

41

<sup>mAE recording will begin with the signing of the ICF.

<sup>nAll prescription and non-prescription medications taken during the trial will be recorded as concomitant medications. Details of prohibited and restricted medications are provided in Section 4.1.

<sup>oCross-titration will occur over a 4-week period in order to bring about a stable transition from previous antipsychotic treatment(s) to oral brexpiprazole.

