## 3.8.3.4 Withdrawal of Consent

All subjects have the right to withdraw their consent from further participation in the trial at any time without prejudice. Subjects cannot withdraw consent for use of data already collected as part of the trial, but only for future participation. The investigator can also discontinue a subject's participation in the trial at any time if medically necessary. Unless the subject provides their written withdrawal of consent or there is other written documentation by the investigator confirming the subject's verbal intent to completely withdraw from the trial, subjects should be followed for all protocol-specified evaluations and assessments, if possible.

Complete withdrawal of consent requires a subject's refusal of ALL of the following methods of follow up (these methods of follow up will also be noted in the trial ICF):

- Participation in all follow-up procedures specified in the protocol (whether in-clinic, by telephone, or by an in-home visit).
- Participation in a subset of protocol specified follow-up procedures (by a frequency schedule and method, as agreed by subject and staff).
- Contact of the subject by trial personnel, even if only by telephone, to assess current medical condition, and obtain necessary medical or laboratory reports relevant to the trial's objectives.
- Contact of alternative person(s) who have been designated in source records as being available to discuss the subject's medical condition, even if only by telephone, mail, or e-mail (eg, family, spouse, partner, legal representative, friend, neighbor, or physician).
- Access to medical information from alternative sources (eg, hospital/clinic medical records, referring doctor's notes, public records, dialysis, transplantation or vital registries, social media sources).

Withdrawal of consent is a critical trial event and therefore should be approached with the same degree of importance and care as is used in initially obtaining informed consent. The reasons for a subject's intended withdrawal need to be completely understood, documented, and managed to protect the rights of the subject and the integrity of the trial. A subject may initially express their desire to interrupt or discontinue IMP administration, which is not equivalent to a complete withdrawal of consent for further participation (see Section 3.8.3.1 and Section 3.8.3.2). A subject may, however, indicate

Confidential - Proprietary Information

63

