7.2 Demographic Characteristics

Baseline demographic characteristics including age, race, ethnicity, gender, weight, height, and body mass index (BMI) will be summarized by descriptive statistics (frequency, mean, median, standard deviation, maximum, minimum, and percentage when applicable) for the Enrolled Sample by parent study treatment group for rollover subjects and overall.

Confidential - Proprietary Information

9

[figure not shown]

Until the information herein is released by Otsuka to the public domain, the contents of this document are Otsuka confidential information and should not be duplicated or re-distributed without prior written consent of Otsuka.

10

10 July 2019

Confidential - Proprietary Information

9 Safety Analysis

The primary safety endpoint analysis is the frequency and severity of AEs in the open-label treatment phase (see Section 9.1). Other standard safety variables to be analyzed include clinical laboratory tests, vital signs, body weight, waist circumference, BMI, 12-lead electrocardiograms (ECGs), and physical examinations.

Safety analyses will be conducted based on the Safety Sample, and summary statistics will be provided by parent study treatment group for rollover subjects and overall, unless otherwise indicated.

Unless otherwise specified, in general, analysis of safety data will be performed on observed case and for last visit.

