Appendix 1 Criteria for Identifying Vital Signs of Potential Clinical Relevance

Variable	Criterion Value ^a	Change Relative to Baseline ^a	
Heart Rate ^b	> 120 bpm < 50 bpm	≥ 15 bpm increase ≥ 15 bpm decrease	
Systolic Blood Pressure ^b	> 180 mmHg < 90 mmHg	≥ 20 mmHg increase ≥ 20 mmHg decrease	
Diastolic Blood Pressure ^b	> 105 mmHg < 50 mmHg	≥ 15 mmHg increase ≥ 15 mmHg decrease	
Orthostatic Hypotension	≥ 20 mmHg decrease in systolic blood pressure and a ≥ 25 bpm increase in heart rate from supine to sitting/standing	Not Applicable (baseline status not considered)	
Weight	-	≥ 7% increase ≥ 7% decrease	

^a In order to be identified as potentially clinically relevant, an on-treatment value must meet the "Criterion Value" and also represent a change from the subject's baseline value of at least the magnitude shown in the "Change Relative to Baseline" column.

^b As defined in "Supplementary Suggestions for Preparing an Integrated Summary of Safety Information in an Original NDA Submission and for Organizing Information in Periodic Safety Updates," FDA Division of Neuropharmacological Drug Products draft (2/27/87).

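### ET safety measurements taken after a new antipsychotic can enter the last-visit and metabolic tables as brexpiprazole results, because the readable SAP sets no on-treatment limit for those tables

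*Protocol*

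**What the plan says.** **Protocol, Table 3.7-1 footnote b.** For a subject who stops before Week 26, "procedures noted for Week 26 must be completed at the ET visit". Three statements follow:

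- A request about order: "Attempts should be made to complete ALL evaluations, particularly efficacy assessments, for the Week 26/ET visit prior to the administration of any new psychotropic medications".
- An exception if that fails: "if the subject receives a new antipsychotic prior to ET procedures, no efficacy assessments should be done".
- A record-keeping rule: "Any prohibited medications started before the end of the trial assessments should be documented as a protocol deviation in the source notes".

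The exception covers efficacy ratings only. Section 3.7.1.2.7 lists what remains at Week 26/ET: physical examination with waist, vital signs with weight, ECG, and fasting laboratory tests including prolactin and HbA1c. Section 3.7.3.4 also wants an ECG at every early termination.

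**Who reaches this point.** Section 3.2.2.1 requires withdrawal of anyone who needs another antipsychotic. Under section 3.8.3.4, unless consent is fully withdrawn, "subjects should be followed for all protocol-specified evaluations and assessments, if possible". The readable protocol gives no maximum interval between the last IMP dose and the ET visit.

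**SAP.** Section 9 states: "Unless otherwise specified, in general, analysis of safety data will be performed on observed case and for last visit". Sections 9.2 to 9.4 then plan summary statistics for laboratory tests, vital signs, weight, BMI, waist and ECG. Section 9.2.2 counts lipid, glucose and metabolic-syndrome abnormalities at any time after baseline. Appendices 1 and 3 are narrower for vital signs, weight and ECG: "In order to be identified as potentially clinically relevant, an on-treatment value must meet the" criterion value as well as the listed change from baseline.

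**The concern.** Footnote b accepts that a rating made after a new antipsychotic no longer describes brexpiprazole. The same reasoning applies to a glucose, lipid, prolactin, waist or QTc value taken at that visit, yet these are still collected, and the readable SAP has no rule that separates them.

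The trial exists to describe the safety of brexpiprazole, with no other antipsychotic permitted in Phase B. It has one arm, so no control group carries the same contamination. If post-switch values enter the last-visit means or the metabolic incidence tables unmarked, a reader cannot tell which results reflect brexpiprazole alone.

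**Working it through.** **1. How much depends on the ET visit (Table 3.7-1).**

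| Measure | Scheduled after baseline | Earlier scheduled value for an early withdrawal |
|---|---|---|
| Weight, blood pressure | Weeks 1, 2, 4, 8, 12, 18, 26/ET | Yes, from Week 1 |
| Laboratory tests, HbA1c, ECG | Weeks 12, 26/ET | Only after Week 12 |
| Waist | Week 26/ET | None |

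Weight is placed at every visit because the vital-signs footnote says: "Vital signs include body weight, body temperature, systolic blood pressure (SBP), diastolic blood pressure (DBP), and heart rate". (The visit text in section 3.7.1.2 names weight only at Week 26/ET; I follow the table.) Metabolic syndrome needs three or more of five criteria at one visit. Waist is one of the five, so Week 26/ET is the only scheduled post-baseline visit at which all five can be assessed.

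**2. Which SAP outputs carry a limit.**

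| Output | Limit in the readable SAP |
|---|---|
| Last-visit and change-from-baseline summaries (9, 9.2 to 9.4) | None |
| Lipid, glucose and metabolic-syndrome incidence (9.2.2) | Called treatment-emergent, but any post-baseline value counts |
| Laboratory clinical relevance (9.2, Appendix 2) | Open-label treatment phase |
| Vital-sign, weight and ECG clinical relevance (Appendices 1 and 3) | On-treatment value |
| QT/QTc categories (9.4) | Open-label treatment phase or treatment period |
| Adverse events (9.1) | Up to 21 days after the last IMP day |

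Only the AE row is tied to the last dose. The limits in rows three to five are not defined in the readable SAP. Protocol section 3.10 defines the treatment period by when subjects are evaluated, whether or not all doses were taken, so it does not settle the matter. The clear gap is the first two rows.

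**3. Scale.** The plan has no figure to reproduce: the sample size is not power-based and no dropout rate is given. From protocol section 3.3.1:

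- Planned non-completers = 384 − 175 = 209.
- Share of those planned = 209 / 384 = 54.4%.

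This is an upper bound on last-visit records that come from an ET visit.

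Let f be the fraction of these 209 whose ET measurements follow a new antipsychotic. The documents do not give f. Then

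- affected share = f × 209 / 384;
- shift in a summary = affected share × d, where d is the new drug's average effect on the measure.

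Both f and d below are assumptions.

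| f | Subjects (f × 209) | Share of 384 | Shift in a rate, d = 10 points | Shift in a rate, d = 30 points | Shift in mean weight, d = 1 kg |
|---|---|---|---|---|---|
| 0% | 0 | 0% | 0 | 0 | 0 |
| 5% | 10.5 | 2.7% | 0.3 | 0.8 | 0.03 kg |
| 10% | 20.9 | 5.4% | 0.5 | 1.6 | 0.05 kg |
| 20% | 41.8 | 10.9% | 1.1 | 3.3 | 0.11 kg |
| 30% | 62.7 | 16.3% | 1.6 | 4.9 | 0.16 kg |
| 50% | 104.5 | 27.2% | 2.7 | 8.2 | 0.27 kg |

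For example, at f = 10%: 0.10 × 209 = 20.9; 20.9 / 384 = 5.4%; 5.4% × 10 points = 0.5 points. The sign of d is also assumed: losing brexpiprazole could move a measure the other way.

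**The case against.** The strongest reply has five parts.

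- **The protocol already asks for the right order.** Sites are to attempt every evaluation, safety included, before any new psychotropic. This stands: post-switch measurement should be the exception. But it is an attempt, and the same footnote provides for its failure.
- **Part of the SAP cannot be read.** The contents list section 5.2 (missing data) and section 10 (conventions), where a last-visit or on-treatment rule would normally sit, but their text is not available. This stands too: one can say only that no readable rule exists.
- **Many tables already carry a treatment limit.** A reader might infer that the safety tables as a whole report another drug's effects as brexpiprazole safety. The documents do not support that. The vital-sign, weight, ECG and laboratory relevance tables and the QT categories are all restricted in some way; what they lack is a readable definition. An ET value also mixes earlier brexpiprazole, its withdrawal and an unknown exposure to the new drug, so it is contaminated rather than a measure of the new drug.
- **The primary endpoint is not involved.** It is the frequency and severity of AEs, which have their own window. What is affected is supporting, descriptive safety data, and weight has earlier scheduled values.
- **The size is unknown.** The figure of 209 assumes that every non-completer attends an ET visit, but section 3.8.3.3 lists death, loss to follow-up and withdrawn consent among the reasons for stopping.

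None of this closes the gap for the last-visit summaries and the section 9.2.2 criteria.

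**Conclusion.** The point holds in a limited form. The protocol collects ET safety measurements after a new antipsychotic, and two groups of readable SAP outputs would count them without distinction: the last-visit change-from-baseline summaries and the any-time-after-baseline metabolic criteria. Exposure is greatest for waist in all non-completers, and for laboratory tests and ECG in those who leave before Week 12.

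The effect lies between zero (every ET visit precedes the new drug) and a ceiling of about 209 of 384 records touched. With assumed shares of 10% to 30% and an assumed 10-point effect, a rate would move by about 0.5 to 1.6 points; with 30 points, by about 1.6 to 4.9. These are illustrations that use 384 as the denominator, not estimates. The conclusion rests on the readable text: if SAP section 5.2 or 10 already separates post-switch values, the SAP part falls away.

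**What to change.** First check SAP sections 5.2 and 10. If they do not already cover this, amend SAP section 9 as follows:

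1. Keep collecting all ET safety data.
2. Derive a flag for any value taken after the first dose of a new antipsychotic or mood stabiliser, using the last IMP date and the concomitant-medication start dates.
3. State one definition of on-treatment, relative to those dates, and apply it to the laboratory, metabolic, vital-sign and ECG tables.
4. Present the last-visit and metabolic tables both with and without flagged values.
5. Report how many subjects and values are flagged.

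The data should already exist. Concomitant medications are recorded at ET (Table 3.7-1), SAP section 9.6 sorts them into before, during and after treatment, and SAP section 6.2 uses an IMP end-date record. No new ET form item is needed. Table 3.7-2 need not change, because it covers de novo subjects only and the SAP states that none were enrolled.

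The cost is some SAP wording, one derived flag and one extra set of tables. In the restricted version some early withdrawals will have no post-baseline laboratory, ECG or waist value. That is why both versions should be shown, rather than the restricted one replacing the other.
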